6.4. Multiple Comparisons/Multiplicity

In order to provide strong control of the Type I error, the key secondary analyses will be tested using a gated testing approach at a 2-sided alpha level of 0.05. If the null hypothesis is rejected for the primary endpoint, key secondary endpoints will be sequentially tested following the gatekeeping hierarchy as shown in [Figure CGAX. 6.1](#).

Following the primary objective, the sequential procedure for key secondary objectives starts with the comparison between treatment groups in the 50% response rate. If that null hypothesis is rejected, then the next comparison in the sequence will be tested, following this same pattern until all hypotheses are tested or until the null hypothesis is accepted for an endpoint, at which point, any further testing would stop for the key secondary objectives.

Abbreviations: MHD = the number of monthly migraine headache days; MSQ RR = Migraine Specific Quality of Life Questionnaire Role Function-Restrictive domain; response = response rate. See Section 5.4 for full definitions of endpoints. Note: All testing will be conducted at a 2-sided alpha of 0.05.

Figure CGAX. 6.1 Gatekeeping sequence for testing of primary and key secondary endpoints.

6.5. Patient Disposition

The number and percentage of ITT patients who complete the study or discontinue early will be tabulated overall for both treatment groups for double-blind treatment (Study Period III), open-label treatment (Study Period IV), and post-treatment follow-up (Study Period V) separately. Reasons for discontinuation will be presented for each period. In addition, subcategories of discontinuation due to subject decision will be summarized.

Patient allocation by investigator will be summarized for all ITT patients.

6.6. Patient Characteristics

The following patient characteristics at baseline will be summarized by treatment group for all ITT patients:

- Demographic (age, gender, race, height, weight, body mass index)
- Duration of migraine illness
- Migraine and/or headache measures per 30-day baseline period
 - number of migraine headache days
 - number of ICHD migraine headache days
 - number of headache days
 - number of moderate to severe headache days
 - number of migraine headache hours
 - number of headache hours

- number of monthly days with acute medication use
 - number of migraine attacks
 - mean severity of migraine headaches
 - number of migraine headache days with nausea and/or vomiting
 - number of migraine headache days with photophobia and phonophobia
 - number of migraine headache days during menstrual period
 - number of migraine headache days with any trigger during menstrual period
 - baseline number of migraine headache day category (<8 versus ≥8)
- Patient Global Impression - Severity
 - MIDAS total score
 - MSQ total score and each domain score
 - Medical history and pre-existing condition

Duration of migraine illness in years will be derived as (inform consent date – migraine start date + 1)/365.25. If multiple migraines were reported in CRF, the earliest start date will be used.

Medical history and pre-existing conditions will be summarized by preferred term (PT) within system organ class (SOC). Medical history is defined as illness(es) that ended prior to the signing of informed consent. Pre-existing conditions are those events that either have an ongoing status of Yes or have an end date on or after informed consent.

6.7. Treatment Compliance

Dosing will occur at monthly study visits. Treatment compliance for each patient will be calculated as the number of completed scheduled dosing visits in which the patient receives an injection, divided by the number of scheduled dosing visits, including any skipped dosing visits at or before the last dosing visit (Visit 9) or early discontinuation visit. For this analysis, partial dose (for example, a patient only received 1 injection instead of 2 at Visit 3 or Visit 7) will be considered as no dose received.

Treatment compliance for SP III and SP IV will be summarized overall and by treatment group.

6.8. Electronic Patient-Reported Outcome Diary Compliance

Electronic patient-reported outcome diary compliance at each 1-month period (including baseline, Month 1, 2, 3, ... till Month 10) as well as for each treatment phase (SP III, SP IV, SP V) will be calculated. Diary compliance at each period is calculated as follows:

$$\frac{\text{Actual number of diary days in the period}}{\text{Expected number of diary days in the period}} * 100$$

Actual number of diary days is calculated as the total number of days with nonmissing answers. Expected number of ePRO diary days is calculated as date of injection (or date of visit for post-treatment follow-up phase) at the end of the interval minus date of injection (or date of visit for post-treatment follow-up phase) at the beginning of the interval +1.

For a patient who discontinues early in the double-blind (SP III) or open-label treatment phase (SP IV) or post-treatment phase (SP V), compliance rate for the last month of that patient will be calculated with a denominator of 30 days (or the actual number of days in the interval if it is greater than 30).

Diary compliance for each period will be summarized overall and by treatment group.

6.9. Concomitant Therapy

The proportion of patients who received concomitant medication collected from eCRFs will be summarized for ITT population for each period separately.

Concomitant therapies for SP III are those which stopped during SP III or continued in SP III. If medication started and stopped on the same day of injection, it will still be considered as concomitant medication for SP III. If a medication started before the first day of injection but stopped on the same day of injection, then it will not be counted as concomitant medication for SP III. Concomitant therapies for SP IV are those which either started, stopped or continued in SP IV.

6.10. Efficacy Analyses

6.10.1. Primary Outcome and Methodology

The primary efficacy measure is the overall mean change from the baseline period in the number of monthly MHDs during the 3-month double-blind treatment phase, and the primary analysis will evaluate the efficacy of galcanezumab (120 mg/month) compared with placebo.

The primary analysis will be performed using a restricted maximum likelihood-based MMRM technique. The analysis will include the fixed categorical effects of treatment, country, month, and treatment-by-month interaction, as well as the continuous fixed covariates of baseline number of MHDs and baseline number of MHDs-by-month interaction.

An unstructured covariance structure will be used to model within-patient errors. The Kenward-Roger (Kenward and Roger 1997) approximation will be used to estimate denominator degrees of freedom. If the model does not converge with both the Hessian and the G matrix being positive definite under the default fitting algorithm used by PROC MIXED, the Fisher scoring algorithm will be implemented by specifying the SCORING option in SAS[®]. If the model still fails to converge, the model will be fit using covariance matrices of the following order specified by a decreasing number of covariance parameters until convergence is met:

- heterogeneous Toeplitz
- heterogeneous first-order autoregressive
- Toeplitz
- first-order autoregressive

When the unstructured covariance matrix is not utilized, the sandwich estimator (Diggle and Kenward 1994) will be used to estimate the standard errors of the fixed effects parameters. The sandwich estimator is implemented by specifying the EMPIRICAL option in SAS[®]. When the

sandwich estimator is utilized, the Kenward-Roger approximation for denominator degrees of freedom cannot be used. Instead, the denominator degrees of freedom will be partitioned into between-subject and within-subject portions by the DDFM=BETWITHIN option in SAS[®]. SAS[®] PROC MIXED will be used to perform the analysis.

The primary endpoint of this study for galcanezumab compared with placebo will be estimated as the treatment main effect from the MMRM analysis model. This provides the average treatment effect across Month 1, Month 2, and Month 3. The Type I error rate for the study will be controlled at a 2-sided 0.05 level (equivalently, 1-sided 0.025 level). Specific details of the testing procedure for the primary outcome and the secondary gatekeeper objectives are provided in Section 6.4.

The results of the statistical tests at each month in the double-blinded treatment phase will be used to assess the onset of effect for galcanezumab compared with placebo. In particular, if the primary efficacy analysis is statistically significant, then the earliest month where the statistically significant improvement is observed and maintained for all the subsequent months during the double-blinded treatment phase will be considered as the period that demonstrated the onset of effect. If the onset of effect occurs in Month 1, the number of weekly migraine headache days in Month 1 will be analyzed to identify the earliest week where the statistically significant improvement is observed and maintained for all the subsequent weeks in Month 1. Details about the analysis for the number of weekly migraine headache days are described in Section 6.10.3.

6.10.2. Sensitivity Analysis for Primary Outcome

Two types of sensitivity analyses are planned to assess the robustness of deviations from the assumptions of primary analysis including normality assumption and missing data assumption.

Missing Data Assumption

Sensitivity analyses will be performed to assess the robustness of the primary analysis conclusions to deviations from missing at random (MAR) assumption. The approach for these analyses is to vary the assumptions of missing data for the primary analysis in a systematic way. Basically, the method will predict the missing outcomes and then add values (Δ_{GMB} , Δ_{P}) to the predictions in the galcanezumab and placebo treatment groups respectively, regardless of the reason the data are missing. This approach is consistent with the sensitivity approach suggested in Permutt (2015). This procedure will be repeated multiple times for different values of (Δ_{GMB} , Δ_{P}) using the following steps:

- 1) Predict the missing outcomes for each treatment via multiple imputation based on observed primary endpoint and baseline values. Such imputation will be carried out using a Markov Chain Monte Carlo method with a Jeffreys prior via SAS[®] PROC MI. Thirty (30) such imputations will be created.
- 2) Add the corresponding Δ value (that is, Δ_{GMB} , Δ_{P}) to the imputed values based on the patient treatment group.
- 3) Conduct the primary analysis separately for each of the 30 imputations.

- 4) Combine the results of these analyses using Rubin's combining rules, as implemented in SAS® PROC MI ANALYZE.

The above steps will be repeated multiple times for different values of (Δ_{GMB} , Δ_{p}) with Δ_{p} ranging from 0 to twice the absolute value of the mean value seen for placebo in the primary analysis, Δ_{GMB} ranging from Δ_{p} to Δ_{p} + absolute value of the mean treatment difference seen within the primary analysis. For example, if the overall mean change from baseline for placebo is -3.6 and the overall treatment difference is -1.5, then Δ_{p} would range from 0 to 7.2 and Δ_{GMB} would range from Δ_{p} to Δ_{p} + 1.5.

Normality Assumption

To assess the robustness of the MMRM results to deviations from normality assumption, a sensitivity analysis for raw number of migraine headache days (total number of migraine headache days for each interval without normalization to 30-day period) will be conducted with a repeated measures negative binomial regression model fitted with SAS PROC GLIMMIX. The model will include treatment, country, month, and treatment-by-month interaction, as well as the continuous fixed covariates of baseline number of monthly migraine headache days and baseline-by-month interaction, log (number of compliant days within each month/30) as the offset in the model. In case of non-convergence, country and/or baseline-by-month interaction may be excluded from the model. Directional consistency of treatment effects from this model and the primary analysis MMRM model as specified in Section 6.10.1 will be examined.

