**Study Period IV:** Patients who complete the double-blind period of this study can opt to enter an open-label period (Study Period IV) for up to 3 months of treatment with 120-mg/month galcanezumab. Following completion of the double-blind period Visit 7 (Month 3) assessments and procedures, patients may enroll in the open-label period of the study and receive open-label study drug. Sites and patients will remain blinded to patients' previous treatment assignments. To preserve blinding at Visit 7, each patient in any treatment group will receive 2 injections: patients randomized to placebo will receive an initial loading dose of 240-mg galcanezumab (2 injections of 120-mg galcanezumab at Visit 7 only); patients randomized to galcanezumab will continue the dose of 120 mg but also receive 2 injections (1 placebo injection and 1 120-mg galcanezumab injection at Visit 7 only). All patients will remain at the office for a 30-minute post-injection observation at this visit. At Visit 8 and Visit 9, all patients will receive a dose of 120-mg galcanezumab. Patients will continue to have efficacy and safety assessed, including daily completion of the ePRO diary and headache medication log (see Section 2, Schedule of Activities). Patients may continue to take their allowed acute migraine or headache medication as in Study Period III.

**Study Period V:** Patients who complete open-label treatment phase or discontinue for any reason during Study Period III or IV must enter into Study Period V for assessment during washout of investigational study drug. During this 4-month phase, sites and patients will remain blinded to patients' treatment assignments. Patients will follow all study procedures during Study Period V but will not receive galcanezumab or placebo. After completion of Visit 10 (Month 6) assessments, if clinically warranted due to a worsening of symptoms, patients may start migraine prevention medications at the discretion of the investigator. The list of allowed preventive medications will be provided separately. At Visit 12 (Month 10), patients will return to the site for their last study visit and be discharged from the study.

Visit 11 (Month 8) will be a virtual visit through telephone by site staff and is to include a review of any spontaneously reported AEs, queries on concomitant medications, and ePRO diary entries since last visit.

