## 8. Discontinuation Criteria

Patients who discontinue the investigational product during the double-blind treatment phase (Study Period III) or open-label treatment phase (Study Period IV) will proceed immediately to Study Period V.

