## 8.2. Discontinuation from the Study

Some possible reasons that may lead to permanent discontinuation include the following:

- Enrollment in any other clinical trial involving an investigational product or enrollment in any other type of medical research judged not to be scientifically or medically compatible with this study
- Participation in the study needs to be stopped for medical, safety, regulatory, or other reasons consistent with applicable laws, regulations, and good clinical practice (GCP)
- Investigator Decision
  - the investigator decides that the patient should be discontinued from the study
  - if the patient, for any reason, requires treatment with another therapeutic agent that has been demonstrated to be effective for the study indication (prevention of migraine) during Study Period III, discontinuation from the study occurs prior to introduction of the new agent
- Subject Decision
  - the patient asks to be withdrawn from the study

Patients discontinuing from the study prematurely for any reason should complete AE and other safety follow-up per Section 2 (Schedule of Activities), Section 9.2 (Adverse Events), and Section 9.4 (Safety) of this protocol.

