5.4. Endpoints

5.4.1. Efficacy endpoints

Migraine and headache endpoints are defined in [Table CGAX. 5.1](#). Each month is defined as a 30-day period with migraine or headache measures normalized from the visit intervals.

Table CGAX. 5.1 Migraine and Headache Endpoint Definitions

Diagnosis	Definition/Criteria
Migraine headache	
A headache, with or without aura, of \geq30 minutes duration with both of the following required features (A and B):
 
A. At least 2 of the following headache characteristics:
 
 • Unilateral location • Pulsatile quality • Moderate or severe pain intensity • Aggravation by or causing avoidance of routine physical activity

	
AND
 
B. During headache at least one of the following:
 
 • Nausea and/or vomiting • Photophobia and phonophobia 
(Definition adapted from the Standard International Headache Society [IHS] International Classification of Headache Disorders (ICHD)-3)

Probable migraine	A headache of ≥ 30 minutes duration, with or without aura, but missing one of the migraine features in the IHS ICHD-3 definition. To be exact, it meets either at least two A criteria and zero B criteria, or one A criteria and at least one B criteria.
Migraine headache day (MHD) (primary objective)	A calendar day on which a migraine or probable migraine occurred.
ICHD migraine headache day	A calendar day on which a migraine occurs.
Migraine headache attack	Beginning on any day a migraine headache or probable migraine headache is recorded and ends when a migraine-free day occurs.
Non-migraine headache	All headaches of at least 30 minutes duration not fulfilling the definition of migraine or probable migraine are classified as non-migraine headaches.
Non-migraine headache day	A calendar day on which a non-migraine headache occurred.
Headache day	A calendar day on which any type of headache occurs (including migraine, probable migraine, and non-migraine headache).
Episodic migraine	4 to 14 migraine headache days and < 15 headache days per 30-day period in the prospective baseline period.

Abbreviations: ICHD = International Classification of Headache Disorders; IHS = International Headache Society; MHD = migraine headache day.

Headache information will be collected via an ePRO diary. Patients will need to enter diary data daily beginning from Visit 2, continuing until Visit 12.

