5.4.1.1. Primary Measure: The Number of Monthly Migraine Headache Days

The primary measure is the number of monthly migraine headache days (MHD). A migraine headache day is defined as a calendar day on which a migraine or probable migraine occurs.

The primary measure of the number of monthly migraine headache days will be summarized from the daily ePRO data for each patient in that period (including 30-40 days of daily data from the baseline period prior to randomization, 3 months of daily data during the double-blind treatment phase, 3 months of daily data during the open-label treatment phase, and 4 months of daily data during the post-treatment phase).

The daily data will be aggregated, and the number of migraine headache days will be provided for each of the 30-day periods. In calculating the number of migraine headache days for each period, if the period is not equal to 30 days, the number of migraine headache days will be adjusted by multiplying the number of migraine headache days by $(30/x)$ where ‘x’ is the total number of non-missing diary days in the period.

For the 4 months of the post-treatment period (Study Period V [SP V]), the monthly interval will be derived as below. Firstly, the 2-month visit interval will be split into two one-month periods for efficacy measures. If the number of days between 2 visits (visit x+1 date - visit x date) is even, the first half will be in the first one-month period and the second half will be in the second one-month period. If the number of days between 2 visits is odd, then the days will be split similarly, but the first one-month period will have 1 day more than the second one-month period. Secondly, after the two month visit intervals are split into two one-month periods, the monthly data will be derived in the same way for each one-month period as for treatment phase. For patients who discontinued early during the post-treatment phase, if the date of discontinuation is within 30 days of previous visit date, all data between the previous visit date and the discontinuation date will go to 1 monthly period; if the date of discontinuation is more than 30 days of the previous visit date, then the first 30 days will be the first monthly period, and the rest will be considered as part of the second monthly period.

This approach to missing ePRO diary data assumes that the rate of migraine headaches per day is the same for days with missing and non-missing ePRO diary days.

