The same approach will also be applied to secondary and exploratory efficacy measures that are derived from ePRO data.

Additionally, if the compliance rate for each monthly interval is $\leq 50\%$, then all endpoints to be derived from the ePRO diary data for that one-month period will be considered missing. For the post-treatment phase, the derived one-month periods (resulting from splitting two-month visit interval) will be treated similarly.

For a patient who discontinues early in the double-blind (Study Period III [SP III]) or open-label treatment phase (Study Period IV [SP IV]) or post-treatment phase (SP V), compliance rate for the last month of that study period will be calculated with a denominator of 30 days (or the actual number of days in the interval if greater than 30). For the rest of months and patients, the compliance rate will be calculated as described in Section 6.8.

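### The delta grid for the primary endpoint is capped at the observed treatment difference, so with similar missingness in both arms it will usually stop short of the tipping point

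*SAP*

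**What the plan says.** SAP 6.10.2 plans one analysis of departures from MAR for the primary endpoint. Missing months are multiply imputed by arm (30 imputations). A shift Δ_P is added to imputed placebo values and Δ_GMB to imputed galcanezumab values, whatever the reason for missingness. The primary analysis is rerun on each completed data set and the results are combined by Rubin's rules. Δ_P runs from 0 to twice the absolute placebo mean. Δ_GMB runs from Δ_P up to Δ_P plus the "absolute value of the mean treatment difference seen within the primary analysis". No rule extends the range. The only other sensitivity analysis of the primary outcome is a negative binomial model, which addresses normality.

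Two rules decide what is missing. If diary compliance in a month is 50% or less, "then all endpoints to be derived from the ePRO diary data for that one-month period will be considered missing" (SAP 5.4.1.1). For a patient who discontinues early, the "compliance rate for the last month of that study period will be calculated with a denominator of 30 days", so a partly observed last month can stay in. Protocol 10.2 and SAP Table CGAX.6.1 restrict the analysis to patients with a baseline and at least one postbaseline observation.

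After stopping drug in the double-blind phase, patients "will proceed immediately to Study Period V" (Protocol 8; Protocol 5.1 agrees). The diary goes on: "Patients will need to enter diary data daily beginning from Visit 2, continuing until Visit 12" (SAP 5.4.1). Study Period V days form their own months: "the 2-month visit interval will be split into two one-month periods for efficacy measures" (SAP 5.4.1.1). Table CGAX.6.1 limits the double-blind efficacy analyses to visits after Visit 3 up to Visit 7.

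**The concern.** The primary MMRM relies on MAR, and the plan allows for 20% discontinuation. A delta analysis is most informative when it shows how large a departure from MAR would change the conclusion. Here the largest differential shift is tied to the effect that was observed. The larger the effect, the larger the cap, but the effect that survives at the cap grows with it. With similar missingness in both arms, a result as strong as the design assumes therefore cannot be lost at the edge of the grid when Δ_P = 0. The reader would learn that the result survives complete loss of benefit among patients with missing months, but would not be told how far beyond that it survives. That distance decides whether a tipping departure is clinically credible.

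**Working it through.** **Inputs.** SAP 5.2: 243 per arm, effect size 0.33, two-sided 0.05, about 90% power, 20% discontinuation. Protocol 5.2: 388 evaluable completers, so 194 per arm. SAP 6.10.2 example: placebo mean −3.6 and difference D = −1.5, so galcanezumab mean −5.1. The missing share f is not given and is assumed below.

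**Plan's own figures.** n per arm = 2(1.96 + 1.2816)²/0.33² = 193, and 193/0.8 gives 242 per arm, or 484 against the stated 486. Power with 194 per arm is 0.90. The example grid also reproduces: 2 × 3.6 = 7.2, and 7.2 + 1.5 = 8.7.

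**Meaning of the cap.** At the cap the average missing-month change is the same in both arms: −3.6 at Δ_P = 0, 0 at Δ_P = 3.6 and +3.6 at Δ_P = 7.2. Return to baseline in both arms (Δ_GMB = 5.1, Δ_P = 3.6) lies on this edge and is covered.

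**Estimate on the grid.** With the standard error held fixed, the estimate is D + f_G·Δ_GMB − f_P·Δ_P. With f_G = f_P = f at the cap it is D(1 − f), so z is (1 − f)Z. With Δ_P = 0, significance is lost at Δ_GMB/|D| = (1 − 1.96/Z)/f. Design Z = 0.33 × √(194/2) = 3.25, and 1 − 1.96/3.25 = 0.397.

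**Range for f.** Patients with no postbaseline month are excluded, so each remaining discontinuer misses at most two of three months. If all 20% leave after Month 1, f = (0 + 20 + 20)/3 = 13.3%. If cumulative dropout is 7, 13.5 and 20% by Months 1, 2 and 3, the 7% with no postbaseline month leave the analysis. The rest miss 0, (13.5 − 7)/93 = 7.0% and (20 − 7)/93 = 14.0%, so f = 7.0%. Months with low diary compliance would add to either figure.

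| Δ_P = 0, equal f | f = 7.0% | f = 13.3% |
|---|---|---|
| Estimate at the cap | −1.40 | −1.30 |
| z at the cap, design Z 3.25 | 3.02 | 2.82 |
| Primary Z below which the cap overturns it, 1.96/(1 − f) | 2.11 | 2.26 |
| Tipping ratio, 0.397/f | 5.7 | 3.0 |
| Tipping Δ_GMB (MHD) | 8.5 | 4.5 |
| Galcanezumab missing-month mean at the tip | +3.4 | −0.6 |

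At Z = 2.5 the ratios are 3.1 and 1.6; at Z = 4.0 they are 7.3 and 3.8. All lie beyond the cap of 1.

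**Simulation with the standard error re-estimated.** Assumptions: 243 per arm, monthly correlation 0.6, 30 imputations, Rubin's rules, no covariates.

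- Staggered 20% dropout in each arm, all dosed patients imputed (f = 13.3%), 60 replicates: z at the cap is 3.03 at Δ_P = 0 and 2.72 at Δ_P = 7.2. The tip is at about 3.2 and 2.6 times the difference.
- The f = 7.0% pattern, 3000 trials, SD of the 3-month mean 4.55 (1.5/0.33): the grid contains a losing pair in 7% of significant trials (2% at Δ_P = 0). The median tipping ratio is 6.0 (interquartile range 4.4 to 7.5).

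**Unequal missingness.** Fixed standard error 1.5/3.25 = 0.4615. With f_G = 13.3% and f_P = 6.7% at Δ_P = 7.2 and the cap, the estimate is −1.5 + 0.133 × 8.7 − 0.067 × 7.2 = −0.825, so z = 1.79 and significance is lost inside the grid. In simulated trials with 20% galcanezumab and 10% placebo dropout under the same population rule, the grid finds a losing pair in 24%.

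**The case against.** The case for the plan is a good one. The cap has a clear clinical meaning, and going beyond it assumes that galcanezumab patients with missing data fare worse than placebo patients with missing data. In absolute terms the grid goes well past return to baseline, to about 3.6 days worse than baseline in both arms. It can show loss of significance when galcanezumab has more missing data or when the primary result is borderline. The f values rest on an assumed dropout pattern. All of this stands.

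A reader might infer more than the documents support, in three ways.

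- *That the grid reports only pass or fail.* SAP 6.10.2 produces a combined estimate at every grid point, so the output is graded. A reader could extrapolate from it roughly, though not exactly, because the standard error grows with the shifts.
- *That 20% dropout means 20% of the data are missing, so the result could tip while galcanezumab patients with missing data are still clearly improved.* That would need every discontinuer to miss all three months. Such patients have no postbaseline month and are excluded by Protocol 10.2 and Table CGAX.6.1. SAP 6.10.2 does not say that they are imputed.
- *That leaving Study Period V diary days out of Months 1 to 3 is a defect in the MAR check.* Using them estimates a treatment-policy effect, which is a different quantity. The planned 486 − 388 = 98 discontinuations include patients who leave the study. For those who need another preventive, "discontinuation from the study occurs prior to introduction of the new agent", so they cannot be recovered.

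**Conclusion.** The point holds as a modest, inexpensive improvement to the robustness assessment. The primary test, its alpha and the sample size are unaffected. With similar missingness in both arms and f of about 7 to 13%, the cap at Δ_P = 0 can overturn only a primary result with Z below about 2.1 to 2.3. At the design Z, the tipping point is about 3 to 6 times the observed difference and is not reported. These sizes assume equal missing shares, a design Z taken from 194 completers per arm, the SAP's illustrative means, and MAR imputations that on average match the observed arm means. A smaller f or a larger Z moves the tip further out; more missing data on galcanezumab brings it in, possibly inside the grid. It is also correct that no rule places Study Period V diary days back into Months 1 to 3, but that supports only an optional supplement.

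**What to change.** Keep the planned grid. Add to SAP 6.10.2 that Δ_GMB is increased beyond Δ_P plus the observed difference, including at Δ_P = 0, until two-sided p < 0.05 is lost. Report the tipping pair beside each arm's observed mean change so that its plausibility can be judged. The cost is SAP wording, a few more runs of the same imputation program, and a tipping point to discuss in the report. If unblinding has already taken place, SAP 6.1 permits further exploratory analyses, and these should be labelled as such.

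Optional supplement, presented as a treatment-policy estimate and not as a test of MAR: for patients who stopped drug in the double-blind phase, place Study Period V diary days that fall within Months 1 to 3 after randomization in the matching month, and rerun the MMRM. Report the number of patients recovered per arm. This uses data already planned for collection and needs one re-windowing step; the number recovered may be small.
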